3.4 Primary Study Endpoints

To determine whether loratedine and famotidine are effective for improving maximum eosinophil counts (eos/hpf) after 12 weeks of therapy with antihistamines in patients with EoE. To assess the safety and tolerability of H1 and H2 antihistamines in subjects with EoE.

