4.4 Early Withdrawal of Subjects

4.4.1 When and How to Withdraw Subjects

Subjects may be withdrawn from the study for safety issues, failure of subject to adhere to protocol requirements, and subject decision to withdraw from the study. Safety issues include adverse effects from the study drugs, or inability to tolerate the study drugs. Failure of subjects to adhere to protocol requirements includes adherence to the medication regimen, absence of follow-up visits, or not completing study questionnaires. As there is a 6 week wash out period prior to study inclusion, patients may have worsening of symptoms of EoE while off prior medications. Patients who have worsening or relapse of symptoms of EoE while enrolled in the trial will be removed from the study.

For patients who do not tolerate the study drug, other treatment alternatives will be offered, including PPIs, corticosteroids, and/or diet modification.

Data will be collected on withdrawn subjects up until the point of study withdrawal. A scheduled follow-up appointment will be ordered in clinic following study withdrawal.

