4.4.2 Data Collection and Follow-up for Withdrawn Subjects

A follow-up appointment will be ordered at the 12 week period after initiation of the study drug or placebo.

5 Study Drug

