8.1 Definitions

Unanticipated Problems Involving Risk to Subjects or Others (UPIRTSO)

Any unanticipated problem or adverse event that meets the following three criteria:

- Serious: Serious problems or events that results in significant harm, (which may be physical, psychological, financial, social, economic, or legal) or increased risk for the subject or others (including individuals who are not research subjects). These include: (1) death; (2) life threatening adverse experience; (3) hospitalization inpatient, new, or prolonged; (4) disability/incapacity persistent or significant; (5) birth defect/anomaly; (6) breach of confidentiality and (7) other problems, events, or new information (i.e. publications, DSMB reports, interim findings, product labeling change) that in the opinion of the local investigator may adversely affect the rights, safety, or welfare of the subjects or others, or substantially compromise the research data, **AND**
- Unanticipated: (i.e. unexpected) problems or events are those that are not already described as potential risks in the protocol, consent document, not listed in the Investigator's Brochure, or not part of an underlying disease. A problem or event is "unanticipated" when it was unforeseeable at the time of its occurrence. A problem or event is "unanticipated" when it occurs at an increased frequency or at an increased severity than expected, AND
- Related: A problem or event is "related" if it is possibly related to the research procedures.

Adverse Event

An untoward or undesirable experience associated with the use of a medical product (i.e. drug, device, biologic) in a patient or research subject.

Serious Adverse Event

Adverse events are classified as serious or non-serious. Serious problems/events can be well defined and include;

- death
- life threatening adverse experience
- hospitalization
- inpatient, new, or prolonged; disability/incapacity
- persistent or significant disability or incapacity
- birth defect/anomaly

and/or per protocol may be problems/events that in the opinion of the sponsor-investigator may have adversely affected the rights, safety, or welfare of the subjects or others, or substantially compromised the research data.

All adverse events that do not meet any of the criteria for serious, should be regarded as **non-serious adverse events**.

Adverse Event Reporting Period

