For this study, the study treatment follow-up period is defined as from the initiation of the study drugs or placebo until the 12 week follow-up appointment.

Preexisting Condition

A preexisting condition is one that is present at the start of the study. A preexisting condition should be recorded as an adverse event if the frequency, intensity, or the character of the condition worsens during the study period.

General Physical Examination Findings

At screening, any clinically significant abnormality should be recorded as a preexisting condition. At the end of the study, any new clinically significant findings/abnormalities that meet the definition of an adverse event must also be recorded and documented as an adverse event.

Post-study Adverse Event

All unresolved adverse events should be followed by the sponsor-investigator until the events are resolved, the subject is lost to follow-up, or the adverse event is otherwise explained. At the last scheduled visit, the sponsor-investigator should instruct each subject to report, to the sponsor-investigator, any subsequent event(s) that the subject, or the subject's personal physician, believes might reasonably be related to participation in this study.

Abnormal Laboratory Values

A clinical laboratory abnormality should be documented as an adverse event if they are considered clinically significant or require therapy.

Hospitalization, Prolonged Hospitalization or Surgery

Any adverse event that results in hospitalization or prolonged hospitalization should be documented and reported as a serious adverse event unless specifically instructed otherwise in this protocol. Any condition responsible for surgery should be documented as an adverse event if the condition meets the criteria for an adverse event.

Neither the condition, hospitalization, prolonged hospitalization, nor surgery are reported as an adverse event in the following circumstances:

• Hospitalization or prolonged hospitalization for diagnostic or elective surgical procedures for a preexisting condition. Surgery should not be reported as an outcome of an adverse event if the purpose of the surgery was elective or diagnostic and the outcome was uneventful.

• Hospitalization or prolonged hospitalization required to allow efficacy measurement for the study.

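### Section 4.4.1 ends all data collection at withdrawal, which conflicts with the adverse-event period in 8.1 and would miss new events before week 12 in at most about 10 of 50 subjects

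*Combined protocol and SAP*

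**What the plan says.** Safety is listed with the eosinophil count as a primary outcome in the Study Summary, and 3.4 gives the aim as "To assess the safety and tolerability of H1 and H2 antihistamines in subjects with EoE".

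Four places bear on how long safety data are collected from someone who withdraws:

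- **4.4.1** sets a stop: "Data will be collected on withdrawn subjects up until the point of study withdrawal". It then adds: "A scheduled follow-up appointment will be ordered in clinic following study withdrawal". No timing is given for that visit, and no data are named.
- **4.4.2**, whose title covers both data collection and follow-up after withdrawal, consists of one sentence: "A follow-up appointment will be ordered at the 12 week period after initiation of the study drug or placebo". Again no data are named.
- **8.1**, under the heading "Adverse Event Reporting Period", states that "the study treatment follow-up period is defined as from the initiation of the study drugs or placebo until the 12 week follow-up appointment". Withdrawn subjects are not excepted. It also states: "All unresolved adverse events should be followed by the sponsor-investigator until the events are resolved, the subject is lost to follow-up", or the event is otherwise explained.
- **8.2** requires all adverse events in the study period to be recorded, and requires the team to ask about them whenever it is in contact with a subject.

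**The concern.** An event that begins after withdrawal but before the 12-week appointment lies inside the 8.1 window and outside the 4.4.1 cut-off. Two coordinators could each follow the protocol and build different safety datasets.

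Withdrawal is not unrelated to safety. Section 4.4.1 allows it for adverse effects and intolerance, and requires removal when EoE symptoms worsen or relapse. Follow-up may therefore be cut short for reasons linked to treatment, and by different amounts in the two arms.

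The rules in 8.5 also use these data. The study stops on any death, and continuation after the first 25 patients is tied to a count of at most two adverse events. With so low a threshold, one event counted or missed can move the count across it.

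**Working it through.** **Step 1. The passages side by side, for a subject withdrawn at week w after starting treatment**

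| Item | Under 4.4.1 | Under 8.1, 8.2 and 4.4.2 |
|---|---|---|
| Event starting before week w | collected | collected |
| Event ongoing at week w | not collected further | followed until resolved, lost or explained (8.1) |
| New event between week w and week 12 | not collected | inside the window; to be recorded (8.1, 8.2) |
| Visit at 12 weeks | no data named | ordered (4.4.2); adverse events asked about (8.2) |

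The 8.1 sentence literally defines a treatment follow-up period. Reading it as the adverse-event window rests on the heading above it. Section 8.2 supports that reading, because it uses the same term as the window for immediate reporting of related serious events.

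Section 8.1 specifically requires follow-up of ongoing events, so the row in real dispute is the third: new events.

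**Step 2. Subjects affected.** Inputs from 7.1: 40 study patients, 20% dropout.

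- Enrolment = 40 / (1 − 0.20) = 50, which reproduces the plan's figure.
- Expected dropouts = 50 − 40 = 10, or 20%.

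Ten is an upper bound, for three reasons:

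- Anyone leaving during the two-week questionnaire run-in (3.1, 6.1) never starts the 8.1 window.
- Anyone lost to follow-up is unobserved under either rule.
- For anyone withdrawn at the 12-week pill count (5.4), the two stops coincide.

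**Step 3. Follow-up at stake.** Planned follow-up = 50 × 12 = 600 patient-weeks, taking the appointment at a nominal 12 weeks. With 10 withdrawals at mean week w, loss = 10 × (12 − w). The documents give no withdrawal times, so w is assumed.

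| Mean week w | Loss (patient-weeks) | Share of 600 |
|---|---|---|
| 3 | 10 × 9 = 90 | 15% |
| 6 | 10 × 6 = 60 | 10% |
| 9 | 10 × 3 = 30 | 5% |

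The extremes are 120 patient-weeks (20%) at w = 0 and none at w = 12.

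**Step 4. The 25-patient look in 8.5.** At the same dropout rate, 0.20 × 25 = 5 subjects. Planned follow-up is 25 × 12 = 300 patient-weeks, once all 25 have reached week 12. The loss at mean week 6 is 5 × 6 = 30, again 10%.

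**The case against.** The best reply is that the plan, read as a whole, already continues safety enquiry. Section 8.2 has the team ask about adverse events at every contact, and withdrawn subjects have two further contacts: the clinic visit in 4.4.1 and the 12-week visit in 4.4.2. The 8.1 window ends at a 12-week appointment. Unresolved events are followed regardless. Even for subjects who revoke authorization, 9.1 has the team seek permission to obtain vital status at the end of the scheduled period. On this view 4.4.1 governs scheduled study data and lacks only an exception clause.

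Much of this stands. It narrows the gap to new events between withdrawal and week 12, and a reader should not infer that the plan abandons the safety follow-up of withdrawn subjects. But it does not remove the conflict. The 4.4.1 sentence is unqualified, and it is the only one that states a data cut-off for these subjects. The week-4 and week-8 contacts in 6.2 and 6.3 are not extended to them.

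A reader might also infer a bias of known direction, flattering the less well tolerated arm. The documents do not support that:

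- They give no split of withdrawals by arm and no event rates.
- Withdrawals for intolerance could predominate on active drug, and withdrawals for worsening symptoms on placebo.
- Section 7.2 specifies no between-arm test of adverse events.
- A subject withdrawn for an adverse effect already has an event on record, so truncation cannot change whether that subject had any event.

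Finally, events after withdrawal occur off study drug, possibly on the alternative treatments that 4.4.1 mentions. Whether they belong in the main safety summary is a fair question of estimand, which is why an on-treatment summary is needed as well.

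**Conclusion.** The conflict is real and in the current text: 4.4.1 on one side; 8.1, 8.2 and 4.4.2 on the other. No passage says which governs. If 4.4.1 is followed, the primary safety outcome loses new adverse events arising between withdrawal and week 12.

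The size is at most about 10 of 50 subjects. The loss is about 5% to 15% of planned patient-weeks, on the assumptions that all 10 are affected and that mean withdrawal falls between weeks 9 and 3. It would be wrong to read this as one in five subjects certainly having two different stops, because 20% is a planning rate that includes people for whom the stops do not differ.

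The truncation can differ by arm, but neither its direction nor the size of any resulting bias can be derived from the documents. It can affect the count and the death rule in 8.5. Nothing here shows that a decision under 8.5 would change.

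**What to change.** Reconcile 4.4.1 with 4.4.2, 8.1 and 8.2 by adding to the data-collection sentence in 4.4.1: *except that adverse events, serious adverse events and vital status are collected for every subject who took at least one dose until the 12-week appointment in 4.4.2, unless consent for contact is withdrawn.* The rest of the sentence stays as it is, so the rule for efficacy data is not altered by this change.

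Collect these data at the post-withdrawal and 12-week appointments already ordered. If the week-4 and week-8 contacts are also to be used for withdrawn subjects, 6.2 and 6.3 must say so.

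In section 7, state that adverse events are summarised in the all-treated population of 7.3 over that common period, with an on-treatment summary alongside.

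The cost is a protocol wording change and a little more follow-up work for at most about 10 subjects. Some off-drug events will enter the total, and the on-treatment summary separates them. Sample size, power and alpha do not change.

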4.4.2 Data Collection and Follow-up for Withdrawn Subjects

A follow-up appointment will be ordered at the 12 week period after initiation of the study drug or placebo.

5 Study Drug

5.1 Description

Loratadine is an oral non-sedating anti-histamine which is highly selective for H1-receptors. H1-antagonists such as loratidine compete with free histamine for binding at H1-receptor sites, which blocks the effects of histamine on H1-receptors in the GI tract through competitive antagonism. Compared to traditional sedating anti-histamines, loratadine is not associated with QT prolongation and has less central nervous system effects. Compared to first generation anti-histamines, loratadine has reduced penetration of the blood brain barrier and greater specificity for the H1 receptor with fewer anti-cholinergic effects. Loratadine is used in the pediatric and adult population for allergic rhinitis and chronic idiopathic urticaria. The standard dose is 10 mg PO once daily. After oral administration, the onset of action occurs within 1-3 hours with peak effects in 8-12 hours and duration of action greater than 24 hours.

Famotidine is an oral histamine type 2 receptor antagonist that inhibits the action of histamine at the histamine H2-receptors, including gastric cells, used for gastrointestinal disorders including gastroesophageal reflux disease and peptic ulcer disease. Oral absorption is approximately 40-45%, and the elimination half-life is 2.5-3.5 hours.

5.2 Treatment Regimen

Famotidine will be taken 40 mg twice daily by mouth for 12 weeks. Loratadine will be taken 10 mg daily by mouth for 12 weeks.

Patients will be randomly assigned to either the treatment or placebo group by a blocked randomization protocol from a computer generated program via the Mayo Clinic statistical team.

5.3 Preparation and Administration of Study Drug

Preparation of the study drug will be performed in the pharmacy for both famotidine and loratadine, and 12 week supplies given to the patient. Famotidine should be taken by mouth 30-60 minutes before the morning and evening meals, and Loratadine should be taken 30-60 minutes before the morning meal.

Similarly, the placebo drugs will be prepared by the pharmacist, with identical instructions for administration as the treatment drugs.

5.4 Subject Compliance Monitoring

In a diary, patients will record time of medication administration before breakfast and evening meal. At the follow-up visit following the 12 week intervention period, a pill count will be performed. Patients who are not more than 70% compliant will be withdrawn from the study.

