5.8.3 Dispensing of Study Drug

On the 12 week follow-up appointment, the treating physician will perform a pill count to document the amount of drug remaining. The pill count will be entered into the study database.

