6.4 Visit 4 (12 week follow-up)

At the 12 week follow-up visit with a physician, we will review the results of the DSQ to be completed for weeks 10-12 of the study drugs. The 12 week follow-up appointment will occur no earlier than 12 weeks after initiation of the study drug and no later than 14 weeks after initiation. The patient will meet with one of the study investigators, and be consented for an EGD. An EGD with esophageal biopsies will be performed. Prior to EGD, a complete blood count and basic

metabolic panel will be ordered as routine per institutional policy. Either KD or DF will perform the EGD in the endoscopy suite, per our institution's standard protocol. Any macroscopic abnormalities seen in the esophagus will be documented and photographed. Any lesions in the upper digestive tract seen on EGD will be biopsied and treated as deemed appropriate by the performing endoscopist. Biopsy specimens will be labeled and placed in a container and labeled with the patient's ID number.

The eosinophil count will be determined by the study pathologist for the post-treatment exam using a previously validated protocol. [2, 3] Four esophageal biopsies will be sampled from both the distal esophagus (3cm above the GE junction) and proximal esophagus (at least 10 cm above the GE junction) to maximize sensitivity of detecting eosinophils.[1] On each biopsy fragment, 5 high-power fields will be examined and the overall peak eosinophil count determined from the field deemed to be most inflamed from all esophageal levels and all high power fields. [4]

Symptomatic improvement will be defined as at least 2 levels on the dysphagia questionnaire.

Study Activity	Week 0 (initial enrollment appointment)	Week 6	Week 10	Weeks 14-16 (follow-up appointment)
Study Agent(s) (weeks 2-14)		X	X	
Informed consent	X			
Physician office visit with medication review and physical exam	X			X
Phone or office visit with study coordinator		X	X	
Pill count		X	X	X
Drug diary		X	X	
Adverse event evaluation		X	X	Х

B-HCG (non-menopausal females)	X		
Dysphagia Symptom Questionnaire (complete weeks 0-2 and 12-14)	X		X
CBC and BMP			X
EGD w/ biopsy			X

7 Statistical Plan

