7.3 Subject Population(s) for Analysis

- All-randomized population: Any subject randomized into the study, regardless of whether they received study drug
- All-treated population: Any subject randomized into the study that received at least one dose of study drug
- Protocol-compliant population: Any subject who was randomized and received the protocol required study drug exposure and required protocol processing
- All-completed population: Only subjects who completed ALL study related procedures and follow-up will be included

8 Safety and Adverse Events

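### The 70% compliance rule withdraws patients at the visit that supplies the only post-treatment biopsy, so the primary comparison may be selected on post-randomisation compliance

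*Combined protocol and SAP*

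**What the plan says.** - **Timing of the count.** Section 5.4: "At the follow-up visit following the 12 week intervention period, a pill count will be performed". Section 5.8.3 agrees: "On the 12 week follow-up appointment, the treating physician will perform a pill count to document the amount of drug remaining". The schedule table in section 6.4 also marks pill counts at study weeks 6 and 10.
- **The rule.** Section 5.4: "Patients who are not more than 70% compliant will be withdrawn from the study". Section 4.4.1 lists failure to adhere to the medication only as a ground on which a patient may be withdrawn.
- **End of the treatment course.** Section 5.2 sets 12 weeks of treatment, and section 6.4 says: "The 12 week follow-up appointment will occur no earlier than 12 weeks after initiation of the study drug".
- **Primary measurement.** Section 3.4 defines efficacy as "improving maximum eosinophil counts (eos/hpf) after 12 weeks of therapy". The post-treatment count comes from Visit 4 (section 6.4): "An EGD with esophageal biopsies will be performed". The same endoscopy is the only post-treatment source for the EREFS.
- **After withdrawal.** Section 4.4.1: "Data will be collected on withdrawn subjects up until the point of study withdrawal". Section 4.4.2 orders a 12-week appointment for withdrawn patients and mentions no endoscopy.
- **Analysis.** Section 7.3 defines four populations, including all randomised patients and a "Protocol-compliant population: Any subject who was randomized and received the protocol required study drug exposure and required protocol processing". It assigns none of them to the primary analysis. The only missing-data provision in section 7.2 is to query missing questionnaires and pathology reports.

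**The concern.** Compliance is observed after randomisation and can be affected by treatment. A patient may take fewer tablets because the drugs are not tolerated, or because symptoms are not improving. If biopsies enter the comparison only for patients above 70%, randomisation no longer protects it, because the two arms may have been filtered differently.

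The timing makes this harder to justify. At the 12-week visit the assigned course is complete, so withdrawal cannot change the exposure that was planned. It can only put the outcome measurement at risk. The plan also leaves open who makes the count. Section 5.8.3 gives it to the treating physician, section 6.4 has the patient meet one of the study investigators, and section 5.7 unblinds the principal investigator and one co-investigator. Nothing stated keeps an unblinded person from making the count that triggers withdrawal.

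At stake are the validity of the between-arm comparison of peak eosinophil counts, the responder proportion and the EREFS, and the number of evaluable biopsies in a trial of 50.

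**Working it through.** **1. Reading the sections together.** A patient at or below 70% at Visit 4 is to be withdrawn (5.4), and data collection then stops (4.4.1).
- If the pill count comes first, no study biopsy is provided for.
- If the endoscopy comes first, a biopsy exists, but the plan does not say whether it is analysed.
- If the week 6 and week 10 counts in the table also trigger the rule, withdrawal comes earlier. The 12-week appointment in section 4.4.2 still names no endoscopy.

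On none of these readings does the text secure an analysed biopsy.

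**2. The plan's own power figures.** Inputs from section 7.1: SD of change 50 eos/hpf, baseline mean 80-110. From section 7.2: two-sided alpha 0.05. A baseline of 100 is assumed, inside the stated range. Normal approximation: power = Φ(δ / (50 × √(2/n)) − 1.96).
- 25 per arm, δ = 40% × 100 = 40: 40/14.14 = 2.83, power 80.7%.
- 16 per arm, δ = 50% × 100 = 50: 50/17.68 = 2.83, power 80.7%.
- Enrolment: 40/(1 − 0.20) = 50.

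The stated 80% and 50 patients reproduce, so the point does not rest on a sample-size error.

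**3. Possible bias with no drug effect.** The documents give no non-compliance rate and no outcomes for non-compliers, so these inputs are assumed. Let a fraction q of an arm be withdrawn, with mean change g eos/hpf worse than the rest of that arm. The retained mean m satisfies overall mean = (1 − q)m + q(m + g), so m lies q × g below the overall mean. The spurious benefit is (q_active − q_placebo) × g.

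| Withdrawn, active / placebo | g = 25 | g = 50 |
|---|---|---|
| 10% / 0% | 2.5 | 5.0 |
| 20% / 0% | 5.0 | 10.0 |
| 20% / 10% | 2.5 | 5.0 |
| equal in both arms | 0 | 0 |

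A 40% difference is 0.40 × 80 = 32 to 0.40 × 110 = 44 eos/hpf. The range 2.5-10 is therefore 2.5/44 = 6% to 10/32 = 31% of it. At the upper end, with 20 active and 25 placebo patients left, SE = 50 × √(1/20 + 1/25) = 15, so the bias is 10/15 = 0.67 SE. Two-sided type I error would be Φ(−1.96 + 0.67) + Φ(−1.96 − 0.67), about 10% instead of 5%.

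**4. Biopsies at risk.** At an assumed 10-20% non-compliance, 0.10 × 50 = 5 to 0.20 × 50 = 10 biopsies. The dropout allowance is 50 − 40 = 10.

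**5. Power for 40 eos/hpf, starting from 20 per arm** (40/15.81 = 2.53, power 71.6%).
- A further 5-20% of both arms removed (19 to 16 per arm): 69.4% to 61.9%.
- All 20 per arm kept, 5-20% of the active arm non-compliant with no effect (δ = 38 to 32): 67.1% to 52.5%.
- The same, with half the effect in non-compliers (δ = 39 to 36): 69.4% to 62.4%.

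Keeping poor compliers does not gain power.

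**The case against.** No section says that the biopsy is skipped or excluded. The order of pill count and endoscopy within Visit 4 is not stated, data up to withdrawal are kept, and an all-randomised population is defined. This stands. A reader might infer that the primary outcome is discarded, or that every efficacy comparison becomes one of compliers only. The text supports only that these biopsies may be lost or left out.

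A reader might also infer that only the biopsy remains at that visit. That is wrong: DSQ review, physical examination, laboratory tests and adverse event evaluation share it, and the endoscopy also supplies the EREFS.

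Nor does the rule hide intolerance. Adverse effects are reviewed at 4 and 8 weeks of treatment (6.2, 6.3), all adverse events are recorded (8.2), and intolerance is a named withdrawal reason (4.4.1).

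The schedule table's earlier pill counts mean the rule might operate before the course ends. That is a conflict to reconcile, and withdrawal would still rest on post-randomisation behaviour.

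Finally, the bias figures rest on assumed inputs, vanish if selection is equal in both arms, and stay below one standard error at the top of the range. Losing 5-10 biopsies also falls within the dropout allowance, though it could use half or all of it. These points limit the claimed size. They do not supply the missing statement of what happens to the biopsy.

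**Conclusion.** The concern holds as a risk that the plan creates and does not control. Sections 5.4, 5.8.3, 6.4, 4.4.1 and 4.4.2 together allow the primary biopsy and EREFS to be lost or left out because of compliance. Sections 7.2 and 7.3 do not repair this, since no population is assigned to the primary analysis and no method is given for missing biopsies. The direction and size of any bias cannot be derived from the documents. The 2.5-10 eos/hpf illustration rests on no drug effect, withdrawal of 10-20% in the active arm only, and outcomes 25-50 eos/hpf worse in those withdrawn. The case for change is validity, not power.

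**What to change.** - **Sections 5.4, 4.4.1 and 4.4.2.** State that, whatever the compliance, the 12-week endoscopy and DSQ data are obtained where the patient agrees and are analysed in the all-randomised population. This is a rule for data collection and analysis; it takes no position on study drug.
- **Section 7.3.** Assign the all-randomised population to the primary analysis. Use the 70% cut-off only to define the Protocol-compliant population, and say whether it applies to each drug (0.7 × 84 = 58.8 and 0.7 × 168 = 117.6 tablets) or to both combined.
- **Section 7.2.** State how missing biopsies are handled.
- **Reconcile** the optional withdrawal for non-adherence in section 4.4.1 with the mandatory one in section 5.4, and the table's pill counts at weeks 6 and 10, contacts that may be by phone, with sections 5.4 and 5.8.3.

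The cost is an amendment to a few sentences; the endoscopy is already scheduled. The statistical cost is that poor compliers can dilute the estimated effect. For 40 eos/hpf at 20 per arm, power falls from 71.6% to 67.1-52.5% if 5-20% of the active arm are non-compliant with no effect. The Protocol-compliant analysis can be reported alongside as supportive, with its selection acknowledged.
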